3.11.10 Logistic regression

The logistic regression of the responder, binary dependent variable, of incidence of patients in both the SPPB/Gait speed Week 24 Completers FAS Analysis Subset with either gait speed (m/sec) ≥ 0.8 or total SPPB score ≥ 9 and a fall, or not will be fitted using PROC LOGISTIC in SAS. The covariates of interest in terms of falls are [REDACTED]

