The risk to patients in this trial will be minimized by compliance with the eligibility criteria, close clinical monitoring and guidance for the investigators provided in the Investigator's Brochure. An adjudication committee will review cardiovascular events to confirm that these events have been evaluated appropriately and diagnosed correctly, while a Data Monitoring Committee (DMC) will monitor safety data from the study and the entire bimagrumab program for potential safety concerns.

As for any other investigational drug, there are unknown risks to bimagrumab, which may be serious and unforeseen.

Benefits

The benefits of bimagrumab treatment in the hip fracture population are still not known. However, it is expected that as seen in healthy volunteers and patients with sIBM, the hip fracture patients will have an increase in muscle mass that may translate to better recovery of lower extremity function and faster return to mobility. Over the course of the study, the number of falls might be reduced, which in turn reduces the risk of traumatic injuries and fractures, including secondary hip fractures.

4 Population

The study population will consist of male and female patients ≥ 60 years old, at time of randomization, who underwent surgical treatment for a low-energy fracture of the proximal femur. The study aims to screen approximately 400 patients. With an estimated screen failure rate of about 40%, approximately 245 patients, with successful surgery after hip fracture, will be randomized in more than 60 centers worldwide. Approximately 200 patients are expected to complete the 24-week treatment epoch and approximately 120 patients the full 48 -week study period.

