9.5.1.3 Falls

The frequency of having at least one fall up to Weeks 24 and 48 will be summarized by treatment group. The time to the first fall may also be assessed using a plot of the Kaplan-Meier product limit estimates and a log rank test provided there are a sufficient number of events. Negative binomial regression may also be used to analyze fall event rates. All details regarding the analyses of falls will be documented in the statistical analysis plan. The numbers of patients meeting the criteria for the responder endpoint derived from SPPB, Gait Speed and incidence of falls by Week 24 and 48 will be summarized by treatment group. A logistic regression may be used to determine the treatment effect.

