The following subsets of patients will be identified for inclusion in the proposed primary and secondary efficacy sensitivity analyses ([Section 2.10.1](#) [Analysis of the primary efficacy variable] and [Section 2.10.2](#) [Analysis of secondary efficacy variables], respectively):

- Total LBM Week 24 Completers FAS Analysis Subset: Patients who have a windowed visit Week 24 total LBM assessment (kg) (primary endpoint) having completed treatment (Week 24 [EOT]).
- SPPB Week 24 Completers FAS Analysis Subset: Patients who have a windowed visit Week 24 SPPB assessment (secondary efficacy endpoint) having completed treatment (Week 24 [EOT]).
- Gait speed Week 24 Completers FAS Analysis Subset: Patients who have a windowed visit Week 24 gait speed assessment (secondary efficacy endpoint) having completed treatment (Week 24 [EOT]).
- SPPB Week 48 Completers FAS Analysis Subset: Patients who have a windowed visit Week 48 SPPB assessment (secondary efficacy endpoint) having completed both the treatment (Week 24 [EOT]) and post-treatment follow-up (Week 48 [EOS]).
- Gait speed Week 48 Completers FAS Analysis Subset: Patients who have a windowed visit Week 48 gait speed assessment (secondary efficacy endpoint) having completed both the treatment (Week 24 [EOT]) and post-treatment follow-up (Week 48 [EOS]).

Per Protocol (PP) analysis set: The PP analysis set will include all FAS patients without major deviations from the protocol procedures at the time of the primary analysis. Major protocol deviations and the definition of the PP analysis set will be identified and finalized based on blinded review of the data, prior to the data extraction for the primary analysis and unblinding of the treatment code.

Modified Per Protocol (PP) analysis set: The Modified PP analysis set will include all FAS patients without a major deviation from the protocol procedures occurring after Week 24 and will be used at the time of the final update analysis. Major protocol deviations and the definition of the modified PP analysis set will be identified and finalized, prior to the data extraction for the final update analysis.

For the definitions of major protocol deviations see [Section 3.10](#) (Protocol deviations).

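### The only visible responder definition (SAP 3.11.10) is ambiguous about falls, no reading of it counts a fall as failure, and its regression is confined to Week 24 completers

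*SAP*

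**What the plan says.** Protocol 9.5.1.3 introduces the endpoint without thresholds, a direction for falls, or a denominator. It plans a summary, for each treatment group, of how many patients satisfy the "criteria for the responder endpoint derived from SPPB, Gait Speed and incidence of falls by Week 24 and 48", and adds: "A logistic regression may be used to determine the treatment effect".

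SAP 3.11.10 is the only visible place that fills in the definition. As to who is analysed, it refers to the "incidence of patients in both the SPPB/Gait speed Week 24 Completers FAS Analysis Subset". Within that set, the outcome separates those "with either gait speed (m/sec) ≥ 0.8 or total SPPB score ≥ 9 and a fall, or not will be fitted". No time window is given for the fall. SAP 2.14 notes only that protocol amendment 4 brought in responder endpoints and the related regression.

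SAP 2.7 admits a patient to each Week 24 completer subset only with a windowed Week 24 assessment and completed treatment, and introduces these subsets for the sensitivity analyses. Protocol 9.2 and SAP 2.10 make the FAS the set for efficacy analyses. On numbers, Protocol section 4 says: "Approximately 200 patients are expected to complete the 24-week treatment epoch", out of about 245 randomised.

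**The concern.** The trial treats fewer falls as a benefit. Protocol 3.2 lists falls among the complications to be avoided, and Protocol 3.6 hopes for a reduction. A responder built from good function and falls should therefore count a fall against the patient. The SAP sentence does not do so, and it is the sentence from which the dependent variable would be programmed. If it were coded as written, a benefit on falls could count against bimagrumab.

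The population is a second problem. Under Protocol 5.5.9, a patient who stops treatment returns about 28 days after the last dose and again four weeks later. That patient contributes fall data but is not in the regression. For lean body mass, gait speed and SPPB, the completer analysis sits beside an FAS analysis (SAP 2.10.1.5 and 2.10.2.4). Here it is the only stated analysis.

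**Working it through.** **1. The plan's own figure.** The documents give no rate or power for the responder endpoint. The nearest figure is the falls power table (SAP Table 2.6), which supplies the fall inputs: placebo rate r0 = 0.30 or 0.40 per year, rate ratio 0.7, dispersion k = 1, 9 months of follow-up, 70 v 140 patients (θ = 2), two-sided 0.05.

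V = (1/t)(1/r0 + 1/(θ·r1)) + (1+θ)k/θ; power = Φ(√n0·|ln RR|/√V − 1.96).

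First row: V = (1/0.75)(1/0.30 + 1/0.42) + 1.5 = 9.12; power = Φ(8.37 × 0.357/3.02 − 1.96) = 16.6%, against the stated 16.3%. All five rows give 16.6, 43.6, 73.5, 19.8 and 52.8%, against 16.3, 42.9, 72.7, 19.5 and 52.0%. The inputs are therefore being read as the plan meant them.

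**2. Proportion with at least one fall by Week 24.** P = 1 − 1/(1 + rate × t), with k = 1 and t = 24/52.

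| Placebo rate per year | Placebo | Active, rate ratio 0.7 |
|---|---|---|
| 0.30 | 1 − 1/1.138 = 12.2% | 8.8% |
| 0.40 | 1 − 1/1.185 = 15.6% | 11.4% |

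Protocol 6.4.5 cites 40-60% falling again within a year. With k = 1 the implied annual rates are 0.40/0.60 = 0.667 and 0.60/0.40 = 1.5, so the Week 24 proportions are 1 − 1/1.308 = 23.5% and 1 − 1/1.692 = 40.9%. The same section places these falls mainly in the first six months, so a constant rate probably understates them.

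**3. The possible readings.** Let G be gait speed ≥ 0.8 m/s, S be SPPB ≥ 9 and F be a fall. The illustration assumes 40% meet G or S in both arms, independence of function and falls, and rates of 0.30 v 0.21. For reading B, half of the 40% are assumed to qualify through gait.

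| Reading | Role of a fall | Placebo | Active |
|---|---|---|---|
| A: (G or S) and F | required | 0.40 × 0.1216 = 4.9% | 0.40 × 0.0884 = 3.5% |
| B: G or (S and F) | helps | 0.20 + 0.20 × 0.1216 = 22.4% | 0.20 + 0.20 × 0.0884 = 21.8% |
| C: (G or S), fall or not | none | 40% | 40% |
| Proposed: (G or S) and no F | failure | 0.40 × 0.8784 = 35.1% | 0.40 × 0.9116 = 36.5% |

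The odds ratio (active to placebo) is about 0.72 under A and 1.06 under the proposed definition. Across 20-60% function the ranges are 0.71-0.72 and 1.05-1.08.

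**4. When function also improves.** Under A, the active arm needs a functional response 0.1216/0.0884 = 1.38 times that of placebo to break even (1.34-1.40 for k from 0 to 2 and placebo rates of 0.30 or 0.40). Take the gait criterion alone, the planned gain of 0.15 m/s, and two gait distributions from SAP Table 2.4:

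| Placebo gait speed, mean (SD) | Reading A | No fall |
|---|---|---|
| 0.77 (0.35) | 5.7 v 5.6%, OR 0.99 | 40.9 v 57.8%, OR 1.98 |
| 0.52 (0.24) | 1.5 v 2.6%, OR 1.78 | 10.7 v 26.8%, OR 3.06 |

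**5. Numbers left.** 200/245 = 81.6%, so 45 of 245 (18.4%) are outside the regression. About 70 × 0.816 = 57 placebo and 140 × 0.816 = 114 active (210 and 700 mg) patients remain. At 40% function, reading A leaves about 3 and 4 responders; the proposed definition gives about 20 and 42.

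**The case against.** The strongest reply is that a garbled sentence should not be treated as a reversed endpoint. A reader might infer that the plan definitely requires a fall for success. The documents do not settle that: reading A is the natural one, but B and C are possible, and a slip for no fall is the likeliest explanation. This stands, and the claim is limited accordingly. It does not rescue the sentence, because none of the three readings counts a fall as failure.

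A reader might also infer that preventing falls must lower the response rate. That holds only at equal function, and only under A and B. The 0.52 (0.24) row above shows a functional gain outweighing the penalty.

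A third tempting inference is that the completer restriction inflates the rate in the arm with more dropout. The documents give no dropout by arm, so neither the direction nor the size of such an effect can be stated. Nor does Protocol 9.5.1.3 contradict a completer denominator, since it names none. The conflict is with the general FAS rule and the stated purpose of the subsets.

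Parts of SAP 2.10 and 3.11.10 are redacted and may hold a fuller definition, its denominator and its Week 48 version. The absence of a visible Week 48 rule is therefore not an error in the plan.

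Finally, the regression is optional and outside the fixed sequence (Protocol 9.5.1.1, SAP 2.10.2.3), and falls are analysed directly by negative binomial regression, log-rank test and odds ratios (SAP 3.11.9, 3.11.4, 3.11.8). A benefit on falls would be seen there. This limits the consequence but does not remove the fault in the definition.

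**Conclusion.** The point holds in limited form. The visible definition is ambiguous, and every reading conflicts with the trial's aim of fewer falls. Under reading A, response is capped at the proportion who fall by Week 24: about 12% or 16% at the planning rates, and about 24-41% on the protocol's cited one-year figures. At equal function and the planned rate ratio of 0.7, a drug that meets its falls target shows an odds ratio of about 0.72 instead of 1.05-1.08. These figures assume k = 1, a constant fall rate and, for the response rates, independence of function and falls; the functional response rates are illustrative.

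Separately, the only stated population leaves out the 18% of patients expected not to complete, with no FAS analysis alongside.

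Primary and controlled secondary inference is unaffected. It is still worth correcting before unblinding, because a change to a dependent variable afterwards would look driven by the data.

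**What to change.** - Define a Week 24 responder as (gait speed ≥ 0.8 m/s or total SPPB ≥ 9 at Week 24) and no fall from first infusion to Week 24, with the brackets written out.
- Make the FAS in randomised groups the main analysis, with a stated rule for missing Week 24 data. Non-response is one option; the multiple-imputation approach already in SAP 3.11.2 is another. Keep the completer analysis as a sensitivity analysis.
- Apply the same definition at Week 48, unless the redacted text already does so.

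The cost is a change of SAP wording, one derived variable and a small amount of extra analysis. Stated response rates may be lower than among completers.

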Appendix 1: Efficacy assessments: Performance and assessment details

SPPB

The short physical performance battery (SPPB) contains five physical functional exercises for the lower extremities divided into three functional components: Total standing balance, gait speed and chair stand. A score will be derived (derived by the [REDACTED] biostatistics team) for each of the three components. In addition, a total SPPB score will also be calculated (derived by the [REDACTED] biostatistics team). The total SPPB score is calculated as the sum of its component scores:

- Total standing balance score.
- Gait speed score.
- Chair stand score.

The total SPPB score will only be calculated if a score is available for each of the three functional component scores.

Standing balance

In each case the lowest possible value is zero (0). Higher values correspond to better functional condition. Total standing balance score is calculated as the sum of the scores of side-by-side stand, semi-tandem stand and tandem stand.

- Side-by-side stand: Held for 10 sec = 1 point, not held for 10 sec or not attempted = 0 points.
- Semi-tandem stand: Held for 10 sec = 1 point, not held for 10 sec or not attempted = 0 points.
- Tandem stand: Held for 10 sec = 2 points, held for 3 to 9.99 sec = 1 point, held for less than 3 sec or not attempted = 0 points.

Handling of missing data: If a test is not done (i.e. test not done is ticked in the eCRF) there will be no imputation of data. If “Side by side stand” is reported as “Not held for 10 seconds”, or “Not attempted”, then the results for “Semi-tandem stand” and “Tandem stand” should be missing. Since the standing balance tests become progressively more difficult with each test, starting from the easiest (“Side-by-side stand”), if the result for the tandem stand or semi-tandem stand is missing the result will be imputed by 0 points, provided that the previous test(s) had been performed. In all other cases there will be no imputation.

Gait speed

Derived gait speed (m/sec) will be assessed as part of the SPPB, over a 4 meter distance of a 6-meter course ([Peel et al \[2012\]](#)). It is the speed (m/sec) at which the 4-meter course is completed and is derived by dividing 4 meters (m) by the time (sec) to complete. Derived gait speed (m/sec) assesses a person's usual walking speed, which is defined as the speed a person normally walks from one place to another (for example, walking from one store to another). The patient will perform two recorded trials of walking across the defined course. The fastest time in seconds (to the nearest 0.01 sec) a patient takes to complete the assessment will need to be selected (the minimum of the two) and used to score the gait speed section of the SPPB eCRF. If only one walk was performed this time will be used. Any walking/mobility aid(s) used during the SPPB gait speed test performance will be captured in the eCRF. The scoring system is as follows:

- Time < 4.82 sec = 4 points.
- Time \geq 4.82 to \leq 6.20 sec = 3 points.
- Time \geq 6.21 to \leq 8.70 sec = 2 points.
- Time > 8.70 sec = 1 point.
- Patient is unable to do the walk = 0 points.

Chair stand

At first the chair stand test will be done one time (singular chair stand test). If the patient used arms to stand or the test could not be completed then the test procedure will be stopped and the score for the test is 0 points. If the patient stood up without using arms the aim of the second part of the test is to stand up five times (repeated chair stand test). The scoring system is as follows:

- Time to complete 5 stands \leq 11.19 sec = 4 points.
- Time to complete 5 stands \geq 11.20 to \leq 13.69 sec = 3 points.
- Time to complete 5 stands \geq 13.70 to \leq 16.69 sec = 2 points.
- Time to complete 5 stands \geq 16.70 to \leq 60 sec = 1 point.
- Patient is unable to complete 5 chair stands or has completed stands in > 60 sec = 0 points.

The total SPPB score will be calculated as the sum of the total standing balance score, gait speed score and chair stand score provided all three component scores are available.

Baseline data of the total SPPB score with the corresponding scores of the three individual component tests: Total standing balance, gait speed, and chair stand will be tabulated in a frequency table. Categories for each of the individual component tests will be:

- 0 points.
- 1 point.
- 2 points.
- 3 points.
- 4 points.

[figure not shown]
Categories for the total SPPB score will be:

[figure not shown]
- 0 to 6 points (Poor performance).

[figure not shown]
- 7 to 9 points (Medium performance).
- 10 to 12 points (Good performance).

[figure not shown]
In addition to the chair stand test score, if the patient attempted the test successfully, the time to complete five stands as reported in seconds will be summarized using descriptive statistics (see [Section 3.2](#) [Precision and summary statistics])

[figure not shown]
If a patient did not attempt a test or failed, the patient will have a missing time for that test.

[figure not shown]

[figure not shown]

[figure not shown]

[figure not shown]

[figure not shown]

[figure not shown]

Appendix 2: Safety laboratory tests: Order of presentation and International system of units

System	Variable	SI Unit
Hematology	Hemoglobin	g/dL
	Hematocrit	Fraction
	Erythrocytes/Red blood cells (RBC)	x10E12/L
	MCV	fL
	MCHC	g/dL
	Leucocytes/White blood cells (WBC)	x10E9/L
	White blood cell differentials:	
	Lymphocytes	% or x10E9/L (abs)
	Monocytes	% or x10E9/L (abs)
	Eosinophils	% or x10E9/L (abs)
	Basophils	% or x10E9/L (abs)
	Neutrophils	% or x10E9/L (abs)
	Reticulocytes	% or x10E9/L (abs)
	Platelets	x10E9/L
Clinical	Total bilirubin	umol/L
	Albumin	g/dL
	Alanine aminotransferase (ALT)	U/L
	Aspartate aminotransferase (AST)	U/L
	Amylase	U/L
	Lipase	U/L
	Cholesterol	mmol/L
	HDL	mmol/L
	Triglycerides	mmol/L
	hsCRP	mg/L
	Plasma haptoglobin	g/dL
	Creatine kinase (CK)	U/L
	Chloride	mmol/L
	Alkaline phosphatase (ALP)	U/L
	GGT	U/L
	Urea (BUN)	mmol/L
	Uric Acid	mmol/L
	eGFR IDMS tr. MDRD	mL/min/SA
	Creatinine	umol/L
	Calculated creatinine clearance	mL/min
	Sodium	mmol/L
	Potassium	mmol/L
	Glucose (fasting)	mmol/L
Magnesium	mmol/L	

[figure not shown]
System	Variable	SI Unit
	Total protein	g/L
	Calcium	mmol/L
	Phosphate	mmol/L
	HbA1c	%
	Pre-albumin	g/dL
	CK-MB	U/L
	CK-MM	U/L
Immunochemistry	T4 (free)*	pmol/L
	Troponin I US*	ug/L
	HBsAg	NA
	HCV AB	NA
	HIV AB	NA
	Myoglobin*	ug/L
	Aldolase*	U/L
	Activin A*	ng/L
	25 OH Vitamin D Total	nmol/l
Urinalysis	Specific gravity	NA
	Ketones	NEGATIVE: Negative, 0, trace POSITIVE: Positive, 1+, 2+, 3+, etc.
	Leukocyte esterase	NEGATIVE: Negative, 0, trace POSITIVE: Positive, 1+, 2+, 3+, etc.
	Total protein	NEGATIVE: Negative, 0, trace POSITIVE: Positive, 1+, 2+, 3+, etc.
	pH	NA
	Glucose	NEGATIVE: Negative, 0, trace POSITIVE: Positive, 1+, 2+, 3+, etc.
	Bilirubin	NEGATIVE: Negative, 0, trace POSITIVE: Positive, 1+, 2+, 3+, etc.
	Hemoglobin	NEGATIVE: Negative, 0, trace POSITIVE: Positive, 1+, 2+, 3+, etc.

[figure not shown]
*Indicates that variable is also measured post-baseline.

Appendix 3: Data collection differences pre- and post-protocol amendment 2

Data recorded pre-protocol amendment 2 for N=14 patients but no longer recorded post-protocol amendment 2 are highlighted in the table below. This data will only be presented in by-patient data listings.

Variable/Category	New/Amended/ Removed	Summary of Modifications Between New versus Old eCRF, Post-protocol Amendment 2
Baseline Physical Activity	New	
In order to assess the overall level of activity and the evolution of walking ability (an indicator of independence) of patients throughout the study, Baseline levels are established for the patients walking ability and use of assistive devices in their day-to-day lives prior to hip fracture.
 
This also includes whether or not physiotherapy was initiated prior to randomization.
 
This evaluation is very important for planning Phase III studies.

Spontaneous Muscle Contraction	New	
Need to account for how many contraction events occurred and how did they present in detail:
 
Need to be able to determine contributing factors and the medical treatment for each event.
 
The severity of contraction will determine the level of medication attention required.
 
Involuntary muscle contractions were reported in 20% to 48% of normal healthy volunteers and patients with sporadic inclusion body myositis (sIBM) treated with bimagrumab (30 mg/kg, i.v.):
 
Contractions were reported as mild in intensity, transient, of short duration, self-limiting and did not require medical treatment.
 
The SMT determined the need to collect more detailed data on pain intensity in order to better characterize the nature of spontaneous muscle contractions and the potential effect and mechanism of action of bimagrumab on these events.

Diarrhea or diarrhea-like events	New	
Need to account for how many events occurred and how did they present in detail such that osmotic and hypermobility events can be distinguished.
 
A 21% incidence rate for diarrhea is currently reported for the BYM 338 program. At the program level at SMT, it was decided to treat diarrhea as an AESI (without adjudication) and collect more details on those events in order to better characterize their nature and the potential effect and mechanism of action of bimagrumab on these events.
 
Diarrhea events will be recorded in the standard Adverse events eCRF and be categorized as AESI diarrhea.
 
• This categorization will then require the AESI eCRF to be completed.
Falls	New	
Falls e-diary was removed as the log pad device was judged not adapted to the study population.
 

		
The different questions and choices for the DVG were based on different publications describing/categorizing falls in their presentation and outcome.
 
The eCRF is set up with repeat capability within each visit.

Vital Signs	Amended	Removed the requirement to measure “Temperature” .
Orthopedic Medical History	Amended	Shortened medical list: May have an impact on the mobility of the patient and their ability to recover from injury : Hip/knee/ankle arthroplasty, hip/knee/ankle arthrodesis, knee/ankle fracture and hip/knee/ankle osteoarthritis
Perioperative Data - Hip Fracture	Amended	
 • Date of assessment is not a relevant variable and is therefore removed. • The screening epoch is defined by the number of days post-surgery it is therefore important to capture date of surgery as a unique variable. • Time between fracture and surgery can be predictive of good/poor outcome it is therefore important to also capture date of fracture. • Questions on blood loss from hip surgery is not going to be relevant and therefore removed. • Questions on correct positioning and wound healing are removed as they are exclusion criteria. 
NOTE: Date of hip fracture and date of surgery questions will be recorded retrospectively for patients enrolled on the original protocol.

Short Physical Performance Battery (SPPB)	Amended	
 • Removed the option for a wheeled walker and rollator as the use of either device is an exclusion criterion.
Falls History	Amended	
 • Amended the falls history lead-in question such that the duration noted is aligned with the subsequent questions i.e. the past 12 months.

Hospitalization	Amended	
 To be able to determine if Hospitalizations are associated with falls eCRF layout was not changed; however the “Reason for Hospitalization” is now coded as: Hospitalization Associated With Falls Other Specify
AE	Amended	
 Removed the lead-in question “Were any adverse events reported?” Added “Require or prolonged hospitalization (N/Y)” to the eCRF Removed “Spontaneous Muscle Contraction Maximum Severity Question” Added “Diarrhea” to the AE classification list.
Prior and Concomitant Medications	Amended	
Dose, unit and frequency will be analyzed for vitamin D as this may have an influence on outcome.
 
Dose, unit and frequency variables will not be analyzed for general medications

Death	Amended	
Death will not be adjudicated for this study.
 
“Tick if cause of death was adjudicated” has been removed.

Transfusion Information	Removed	

AE: Adverse event. AESI: Adverse event of special interest. DVG: Discrete value group. eCRF: Electronic case report form. [REDACTED] SMT: Safety management team. SPPB: Short physical performance battery. Blue highlighted information: Items only collected for pre-amendment 2 and subsequently only listed.

Appendix 4: Data collection differences pre- and post-protocol amendment 3

Data recorded pre-protocol amendment 3 for patients but no longer recorded post-protocol amendment 3 are highlighted in the table below. This data will only be presented in by-patient data listings.

Variable/Category	New/Amended/ Removed	Summary of Modifications Between New versus Old eCRF, Post-protocol Amendment 3
Echocardiography	Removed	
Will only be utilized for patients who enrolled before Amendment #3. Those enrolled prior to the amendment will still have to complete their echo monitoring, including assessment at Week 48, if the Week 24 assessment indicated clinically meaningful abnormality. Instruction as to when the patient is required to undergo an additional assessment at Week 48 has also been included.
 
The requirement of re-assessing QTcF by local ECG reading at baseline has been omitted; eligibility will only be assessed at screening utilizing central reading.

Blue highlighted information: Items only collected for pre-amendment 3 and subsequently only listed.

4 References

References are available upon request.

Bretz, et al 2005, Pinheiro, et al 2013, Qualification Opinion on MCP-Mod EMA 2014.

[name], [name], [name] (2014) CBYM338D2201 Study Procedures Manual.

